#### 6 STUDY PROCEDURES

#### 6.1 Screening (Visit 1) From Day -10 up to Day -7

Subjects will be screened 7-10 days prior to administration of the investigational product to confirm that they meet the subject selection criteria for the study. The investigator (or an appropriate delegate at the investigator site) will obtain informed consent from each subject.

The following procedures will be completed and recorded in source documents:

- Obtain written informed consent.
- Review Inclusion and Exclusion criteria.
- Collect demography (age, gender).
- Collect height and weight.
- Obtain medical history, including history of illegal drug and alcohol use.
- Obtain complete medication history of all prescription or nonprescription drugs, and dietary and herbal supplements taken within 3 months prior to Visit 1.
- Conduct full physical examination and collect vital signs (blood pressure (BP), pulse rate (PR), RR, temperature).
- Collect standard 12-lead electrocardiogram (ECG).
- Instruct subject in ceasing all NSAID treatment and in use of rescue medication
- Instruct subject on study requirements
- Assess eligibility.
- Dispense rescue medication
- Following at least a 4-hour fast, collect blood and urine specimens for the following:
  - Safety laboratory tests;
  - Urine drug screening;
  - Serum FSH concentration for any female who has been amenorrheic for at least 12 consecutive months;
  - Urine β-hCG for all females of childbearing potential.
- Review any AEs

GlaxoSmithKline Consumer Healthcare Confidential Template Version Effective: 22-Jun-2017 Page **39** of **71**  To prepare for study participation, subjects will be instructed on the use of the Lifestyle Guidelines and Concomitant Treatment(s) sections of the protocol.

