#### **Events Meeting the AE Definition:**

GlaxoSmithKline Consumer Healthcare Confidential Template Version Effective: 22-Jun-2017

- Any abnormal laboratory test results (hematology, clinical chemistry, or urinalysis) or
  other safety assessments (eg, ECG, radiological scans, vital sign measurements),
  including those that worsen from baseline, considered clinically significant in the
  medical and scientific judgment of the investigator (ie, not related to progression of
  underlying disease).
- Exacerbation of a chronic or intermittent pre-existing condition including either an increase in frequency and/or intensity of the condition.
- New conditions detected or diagnosed after signing ICF even though it may have been present before the start of the study.
- Signs, symptoms, or the clinical sequelae of a suspected drug-drug interaction.
- Signs, symptoms, or the clinical sequelae of a suspected overdose of either study treatment or a concomitant medication. Overdose per se will not be reported as an AE/SAE unless it is an intentional overdose taken with possible suicidal/self-harming intent. Such overdoses should be reported regardless of sequelae.

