#### 8.2 Reporting Period

#### 8.2.1 Adverse Event

AEs (serious and nonserious) will be collected from the time the subject has signed informed consent and until 28 days following last administration of the investigational product.

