#### 8.7 Follow-up of Adverse Events and Serious Adverse Events

After the initial report, the investigator is required to proactively follow up with each subject and provide further information on the subject's condition.

All AEs/SAEs will be followed until resolution, until the condition stabilizes, until the event is otherwise explained, or until the subject is lost to follow-up.

The investigator is obligated to perform or arrange for the conduct of supplemental measurements and/or evaluations as may be indicated or as requested by GSK to elucidate as fully as possible the nature and/or causality of the AE or SAE. This may include additional laboratory tests or investigations, histopathological examinations, or consultation with other health care professionals.

New or updated information will be recorded in the originally completed CRF.

The investigator will submit any updated SAE data to GSK within 24 hours of receipt of the information.

Investigators are not obliged to actively seek AEs or SAEs in former subjects. However, if the investigator learns of any SAE, including the death, at any time after a subject has been discharged from the study, and considers the event reasonably related to the investigational product or study participation, the investigator will promptly notify GSK by emailing the information to the GSK CH Clinical Operations Safety Reporting email box (PPD). The GSK CH Study Manager or designee will be responsible for

GlaxoSmithKline Consumer Healthcare Confidential Template Version Effective: 22-Jun-2017 Page **56** of **71**  forwarding the information to the Case Management Group, Global Clinical Safety and Pharmacovigilance group mailbox at GSK).

The investigator will submit any updated SAE data to GSK within the designated reporting time frames.

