#### 10.2.7 Safety Analysis(es)

Safety variables will be summarized on the safety population.

Exposure to study drug (number of applications, total weight of gel used) will be summarized by treatment group.

Treatment Emergent adverse events (TEAE, i.e. AEs that start or worsen after first study treatment administration) will be summarized by presenting, for each treatment group, the number and percentage of subjects having any TEAE, any TEAE in each MedDRA primary System Organ Class (SOC) and having each individual TEAE (using MedDRA preferred term). This will be done separately for all TEAEs and for TEAEs that are suspected to be drug-related. All TEAEs will also be tabulated in corresponding fashion by severity. Any other information collected (e.g. action taken, duration, outcome, seriousness) will be listed as appropriate.

All adverse events (prior to treatment and treatment emergent) will be listed.

Chemistry and hematology results at screening, Visit 3 and at Visit 4 will be summarized by the mean, standard deviation, median, minimum and maximum values in each treatment group. Shift tables (between baseline and Visit 3, between Visit 3 and Visit 4) will also be presented. Laboratory normal ranges and all laboratory test results will be listed.

Vital signs (systolic and diastolic blood pressure, pulse rate, respiratory rate) recorded at Visit 3 and changes in vital signs from Visit 2 (baseline) to Visit 3 will be summarized by the mean,

GlaxoSmithKline Consumer Healthcare Confidential Template Version Effective: 22-Jun-2017 Page **61** of **71** 

standard deviation, median, minimum and maximum values in each treatment group. Vital signs at each assessment will also be listed.

ECG results at Visit 3 and Visit 4 will be summarised.

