## 4.7 Analysis of Safety

### 4.7.1 Adverse Events and Serious Adverse Events

Adverse events (AEs) will be summarized (Table 14.3.1.1) by presenting, for each treatment group, the number and percentage of subjects having any AE, any Treatment Emergent adverse events (TEAE), any serious TEAE, any study drug-related TEAE, any study drug-related serious TEAE, any TEAE leading to treatment discontinuation or study discontinuation, or any AE leading to death. TEAE is defined as an AE that starts on or after the date of first study treatment. For an AE with an incomplete start date where the day is missing while the year and month are present and the same as the date of first study treatment administration, the date of first study treatment will be assumed to be the AE start date.

TEAEs will be summarized by presenting, for each treatment group, the number and percentage of subjects having any TEAE, any TEAE in each MedDRA primary system organ class (SOC) and having each individual TEAE (using MedDRA preferred term).

This will be done separately for all TEAEs by SOC/Preferred term (Table 14.3.1.2) and for TEAEs that are suspected to be drug-related by SOC/Preferred term (Table 14.3.1.4). All TEAEs will also be tabulated in corresponding fashion by SOC/Preferred term/Intensity (Table 14.3.1.3 and Table 14.3.1.5). Any other information collected (e.g. action taken, duration, outcome, seriousness) will be listed as appropriate.

Additionally, all adverse events will be listed (listing 16.2.7.1).

Deaths occurring during treatment (if any) will be listed by treatment, including the date and study day of death, and the principal cause of death (listing 14.3.2.1). Non-fatal serious AEs and TEAEs leading to study treatment discontinuation will be listed (listing 14.3.2.2 and Listing 14.3.2.3).

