## 5 Changes to the Protocol Defined Statistical Analysis Plan

Any changes from the originally planned statistical analysis specified in the protocol are outlined in Table 5-1.

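### SAP 4.7.1 defines a treatment-emergent AE by start date alone, dropping the protocol's worsening criterion without declaring the change

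*SAP*

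**What the plan says.** The protocol gives its definition in the summary and again in section 10.2.7: "Treatment Emergent adverse events (TEAE, i.e. AEs that start or worsen after first study treatment administration". An event qualifies either by starting or by worsening after the first application.

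SAP 4.7.1 has one criterion: "TEAE is defined as an AE that starts on or after the date of first study treatment". It adds a partial-date rule. If the start day is missing and the month and year match those of first treatment, the start is set to the date of first treatment. No other part of the SAP counts worsening.

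SAP section 5 says: "Any changes from the originally planned statistical analysis specified in the protocol are outlined in Table 5-1". That table has two entries, the added per-protocol pharmacodynamic analyses and the replacement rules for values below the limit of quantification. The TEAE definition is not among them.

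On timing, protocol 8.2.1 says: "AEs (serious and nonserious) will be collected from the time the subject has signed informed consent". Protocol 6.1 says: "Subjects will be screened 7-10 days prior to administration of the investigational product". On follow-up of an event already reported, protocol 8.7 says: "New or updated information will be recorded in the originally completed CRF".

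**The concern.** The two documents classify the same event differently, and the SAP is the one that will be programmed. The design leaves a period of 7 to 10 days, after consent and before any gel, in which an AE can begin and be recorded. Dosing then runs for 7 days, or up to 14 if surgery is delayed, and surgery follows. An event that is mild in washout can therefore become moderate or severe on treatment or after the operation.

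At stake are the safety tables on which the arms will be compared descriptively: all TEAEs, drug-related TEAEs, and both of these by intensity. The overview rows for serious, drug-related and discontinuation-related TEAEs are affected too. With groups this small, one subject moves a percentage visibly. A reader of the study report who relies on the protocol definition would also not know that a narrower one had been applied.

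**Working it through.** The plan states no figure to reproduce, so the check is a comparison of texts followed by a scale calculation.

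**Step 1. Apply both definitions to the same events.**

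| Event | Protocol 10.2.7 | SAP 4.7.1 |
|---|---|---|
| Starts Day 3 | TEAE | TEAE |
| Starts Day -4, mild, unchanged | Not a TEAE | Not a TEAE |
| Starts Day -4, mild; severe on Day 5, same record updated | TEAE (worsened) | Not a TEAE (start date precedes Day 1) |
| Starts Day -4, mild; worsening on Day 5 entered as a new AE | TEAE | TEAE (new start date) |
| Starts in washout, start day missing, same month and year as first dose; worsens later | TEAE (worsened) | TEAE (start imputed to first dose) |

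The definitions part only in the third row.

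**Step 2. Ask whether the third row can arise.** It needs an AE recorded before dosing, which collection from consent allows. It also needs the worsening to be entered as an update. Section 8.7 directs new information to the existing CRF, and nothing in section 8 requires a second AE entry when a recorded AE worsens. The row is therefore possible under the documents, though not certain to occur.

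**Step 3. Trace the outputs in SAP 4.7.1.** A third-row event is absent from Tables 14.3.1.2 to 14.3.1.5 and from every TEAE row of Table 14.3.1.1. It is present in the any-AE row of Table 14.3.1.1 and in Listing 16.2.7.1. If serious and non-fatal, it is also in the serious-AE listing. The overview row for AEs leading to death is not restricted to TEAEs.

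**Step 4. Scale.** Inputs: about 50 randomised 2:1 (protocol 10.1 and section 3), and the assumption that all are dosed and so enter the safety population.

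- Active: 50 × 2/3 ≈ 33; one subject = 1/33 = 3.0 percentage points.
- Placebo: 50 × 1/3 ≈ 17; one subject = 1/17 = 5.9 percentage points.
- If only the 30 and 15 subjects planned as evaluable were dosed: 1/30 = 3.3 and 1/15 = 6.7 points.

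These figures apply to the any-TEAE row only when the missed subject has no other TEAE. Otherwise only the system organ class, preferred-term, intensity or subset rows change. The expected number of such subjects cannot be derived from the documents.

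**The case against.** The strongest reply is that the SAP rule may lose little or nothing in practice. Several parts of it stand.

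- A reader might infer from section 8.7 that a worsening always keeps its pre-dose start date, so that it can never count. The text does not go that far. It speaks of the CRF and says nothing about onset dates or severity changes. Section 9.2 uses CRF for the whole record on a subject, and section 8.3.1 refers to AE pages within it. Adding a new AE entry would be compatible with 8.7. CRF completion instructions are not in the documents.
- The protocol's AE definition covers some worsening directly. Its list of qualifying events includes "Exacerbation of a chronic or intermittent pre-existing condition including either an increase in frequency and/or intensity of the condition". Where such an exacerbation is reported as its own AE after Day 1, it meets the SAP rule.
- The partial-date rule brings some washout events back in.
- The most obvious event on stopping NSAIDs is knee pain. The protocol excludes symptoms of the disease under study from AEs unless the investigator judges them worse than expected.
- Safety is summarised descriptively, with no test planned, and the same rule applies to both arms.

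These points limit how often the discrepancy matters. They do not remove it. None of them requires a new record when an AE already recorded in washout worsens, and none explains why the SAP departs from the protocol without saying so.

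**Conclusion.** The point holds as an undeclared narrowing of the protocol's TEAE definition. Its practical effect is confined to AEs recorded before first dose that worsen afterwards and are updated in place. Those events drop out of the TEAE summaries but not out of reporting altogether.

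The size is unknown and probably small: about 3 points on active or 6 on placebo per missed subject with no other TEAE, assuming about 33 and 17 dosed. The documents do not support a claim that every washout event that worsens is lost, or that serious worsening would go unseen.

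The correction is still worth making before the tables are produced, because the conflict is explicit and cheap to remove.

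**What to change.** In SAP 4.7.1, restore the protocol definition, so that a TEAE is an AE that starts or worsens after first study treatment administration. Add one sentence saying that worsening is identified either from a new AE record or from a dated increase in severity on the existing record, whichever the CRF supports. The protocol speaks only of worsening, so restoring its definition does not require adding changes in seriousness or causality.

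The SAP's date-based wording also admits events on Day 1 before the first application, which the protocol's does not. If AE clock times are not collected, keep the date convention for Day 1 and declare it.

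If the sponsor prefers the narrower rule, the alternative is to enter it in Table 5-1 with a reason.

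The cost is a sentence or two in the SAP and minor programming. Reported TEAE counts may rise slightly.

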<sup>f One PK sample will be taken prior to last dose on Day 7. Two PK samples will be taken after administration of the last dose: one sample prior to surgery and one sample during surgery

<sup>9 Doses should occur at least 8 hours apart and twice per day

<sup>h The first dose of study treatment will be applied after washout, at the clinic, at Visit 2. It will be administered by a study nurse at the study site, following baseline assessments.

For PK and PD biomarkers

<sup>j Adverse events will be recorded from the signing of informed consent.

kWill take place between final dosing with study treatment and prior to surgery

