### 4.3.3 Prior and Concomitant Medication

Any medications taken by subject within 90 days before the screening visit (Visit 1) and up to the last study visit (Visit 4) during the study will be recorded in the case report form (CRF).

All medications will be coded using the GSK Drug coding dictionary (GSKDRUG), which will be updated whenever available throughout the life of the study.

For purposes of analysis, prior medications are defined as any medications with a stop date that is prior to the initial study drug dosing date (Day 1) and concomitant medications are defined as any medications with a start date on or after the initial study drug dosing date (Day 1) or any medications with a start date prior to the initial study drug dosing date and a stop date after the initial study dosing date.

> GlaxoSmithKline Consumer Healthcare Confidential Page 13 of 22

For medications with partial start or stop dates, the partial dates will be imputed according to Table 4-1 and then will be categorized as prior medication or concomitant medication according to the definitions. Medications with completely missing dates will be included in the concomitant medication summary.

Imputation rules for the start or stop date of missing or incomplete medications are presented in Table 4-1.

	Missing	Imputation	Exception
Start date (concomitant medication)	Day	01	Default to Study Day 1 if an event starts the same year and month as Day 1 and the stop date contains a full date and the stop date is later than Day 1; Otherwise If the stop date is prior to Day 1, default to 1 day prior to the stop date
	Day/Month	01Jan	Default to Study Day 1 if an event started the same year as Day1 and the stop date contains a full date and the stop date is later than Day 1; Otherwise If the stop date is prior to Day 1, default to 1 day prior to the stop date
	Day/Month/Year	No imputation	Assume start prior to study entry.
Stop date (concomitant medication)	Day	Last day of the month	Default to the End of Study Date if the concomitant medication stopped the same year and month as the End of Study Date.
	Day/Month	31DEC	Default to the End of Study Date if the concomitant medication stopped the same year as the End of Study Date.
	Day/Month/Year	No imputation	Assume stops after study

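### SAP 4.7.1 imputes AE start dates without checking the stop date, so an AE with a missing start day in the first-dose month and a recorded stop before first dose is counted as treatment-emergent

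*SAP*

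**What the plan says.** SAP 4.7.1 gives one rule for incomplete AE start dates. It applies when "the day is missing while the year and month are present and the same as the date of first study treatment administration", and then "the date of first study treatment will be assumed to be the AE start date". No condition on the stop date is attached. The same section classifies by start date alone: "TEAE is defined as an AE that starts on or after the date of first study treatment". An AE imputed under this rule is therefore always treatment-emergent.

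Protocol 10.2.7 describes TEAEs as "AEs that start or worsen after first study treatment administration" and treats events before treatment as a separate class in the listing of all AEs. SAP Table 5-1, which records departures from the protocol analysis, mentions no change on this point.

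Pre-dose events will be in the database. Protocol 8.2.1 states that "AEs (serious and nonserious) will be collected from the time the subject has signed informed consent", and the Schedule of Activities repeats it in a footnote. Protocol 6.1 sets the interval: "Subjects will be screened 7-10 days prior to administration of the investigational product".

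For medications, SAP 4.3.3 defines as prior any medication that stopped before Day 1. Table 4-1 adds, for incomplete start dates, "If the stop date is prior to Day 1, default to 1 day prior to the stop date".

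**The concern.** First dose is a sensible default when nothing is known about when in the month an AE began. It is not sensible when the record already shows that the AE was over before first dose. In that case the rule overrides a recorded date with an assumed one, gives a start later than the stop, and places a washout event in the TEAE tables.

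What is at stake is the accuracy of the descriptive safety tables: the overview (Table 14.3.1.1), the table by system organ class and preferred term (14.3.1.2) and the table by intensity (14.3.1.3). The arms are small, so one misplaced subject is visible in a percentage. A negative duration in the AE listing would also raise questions when the report is reviewed.

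**Working it through.** The documents state no figure for this rule, so there is none to reproduce. The check applies the rule to a case and then sizes one error.

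**1. Conditions for the error.** All four must hold:
- the start day is missing;
- the start month and year are known;
- they equal the month and year of first dose;
- a complete stop date before first dose is recorded.

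If any one fails, this error does not arise.

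**2. Worked case (assumed dates).** First dose 15 June; AE start June, day unknown; AE stop 12 June.
- Rule as written: start = 15 June. Since 15 June is on or after first dose, the event is a TEAE. Duration = stop − start + 1 = 12 − 15 + 1 = −2 days, which is impossible.
- With a stop-date check: 12 June is before 15 June, so the event is not a TEAE. If a start date is also imputed in the manner of Table 4-1, it is 11 June, and the duration is 12 − 11 + 1 = 2 days.

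**3. Against the protocol definition.** An event that ended on 12 June neither started nor worsened after 15 June. It fails the definition in Protocol 10.2.7. It also fails the SAP's own start-date definition on any start date compatible with its stop.

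**4. How often the month condition is met (reach of the rule, not its error rate).** Assume Day 1 is uniform over a 365-day year. A day k days before Day 1 lies in the same calendar month with probability 1 − 12k/365 for these short lags. Weighting all washout days equally:
- 7-day washout: mean k = 4, so 1 − 48/365 = 0.868, about 87%;
- 10-day washout: mean k = 5.5, so 1 − 66/365 = 0.819, about 82%.

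The month condition would therefore usually hold for a washout AE. This says nothing about how many AEs lack a start day or have a recorded pre-dose stop.

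**5. Size of one error.** The plan randomizes about 50 subjects 2:1 (Protocol 3; SAP 1.1).
- Active: 50 × 2/3 ≈ 33, so one subject is 1/33 = 3.0 percentage points.
- Placebo: 50 × 1/3 ≈ 17, so one subject is 1/17 = 5.9 percentage points.

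These apply to a table row in which the subject has no other event. If the subject already counts in that row, the percentage does not move.

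**The case against.** The case for leaving the rule alone has several parts.

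- **The trigger is narrow.** The site must know the day an event ended but not the day it began, within a window of 7 to 10 days. AEs are reviewed at Visit 2 before randomization (Protocol 6.2.1). Edit checks, manual queries and monitor review (Protocol 9.3.1), and cleaning before lock (SAP 2.2), are chances to recover the missing day. This stands as a reason to expect few cases. It does not guarantee none.
- **The default is conservative.** It over-counts TEAEs and is the same in both arms. This stands where the stop date is missing, ongoing, or on or after Day 1. It does not stand where the recorded stop rules out a post-dose start.
- **The consequence is low.** AE summaries are descriptive, and all AEs appear in Listing 16.2.7.1, so an affected event stays traceable. This stands, and it limits the severity.

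Four stronger readings are tempting and should not be drawn:
- That washout AEs in general are counted as TEAEs. Only those meeting all four conditions above are.
- That the 82% to 87% is a misclassification rate. It is only the chance that the calendar months match.
- That Table 4-1 contains a safeguard against the same misclassification which was left out for AEs. Under SAP 4.3.3 the stop date already makes a medication prior, whatever its start. The Table 4-1 exception only keeps the imputed start consistent with the stop. It is a precedent for consistency and no more.
- That symptom flares after stopping NSAIDs would fill the TEAE tables. Protocol 8.1.1 keeps expected signs and symptoms of the disease under study out of the AE definition unless they are judged more severe than expected.

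**Conclusion.** The rule is wrong as written in a narrow case. An AE with a missing start day in the month of first dose, and a complete stop date before first dose, is given a start after its stop and is counted as treatment-emergent, contrary to Protocol 10.2.7. No other section of either document corrects this.

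The severity is minor. The number of such records cannot be derived from the documents and is probably small. Each one moves a TEAE row by about 3.0 points (active) or 5.9 points (placebo), assuming about 33 and 17 treated subjects and no other event for that subject in the row. The primary, secondary and exploratory endpoints are unaffected.

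**What to change.** Add to the imputation sentence in SAP 4.7.1:

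> unless the AE has a complete stop date before the date of first study treatment, in which case the AE is not treatment-emergent.

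This agrees with how SAP 4.3.3 treats medications that stop before Day 1, and it leaves the first-dose default in place everywhere else. A complete stop date is the only form worth naming. A stop known only by month and year could be certain to precede first dose only by lying in an earlier month, which would be before the AE's own start month.

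It is cleaner to exclude the AE by classification than to impute a start one day before the stop. For an AE that stopped on the 1st of the month, that imputation would move the start into the previous month and contradict the recorded start month.

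The cost is one clause in the SAP and one line of derivation code. No new data are needed beyond the AE stop date.
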